**Table 1. Intervention Events According to Timeline**

EVENT	PAC VISIT	DAY AFTER PAC VISIT	DAY OF ADMISSION	POSTOPERATIVE DAY 1
Recruitment	X			
Consent	X			
Placement of monitor	X		X	
Monitor removal		X		X

**Outcome Measure(s)**

- Primary outcomes:
  - Phase I: Quantitate the data capture rate and how reliable our monitor return rate is in this setting.
  - Phase 2: Quantitate the data capture rate in this setting for the perioperative period.
- Secondary:
  - Assess the prevalence of alterations in VS (HR, RR, SaO2, BP, Cardiac Output, Stroke Volume, and HRV preoperatively) in a group of our highest acuity patients (top quartile of our internal PAC risk score) undergoing non-cardiac surgical procedures requiring at least an overnight admission. See Table 2 for ranges.

**Table 2. Data Sorted into Ranges for each parameter**

Heart rate (bpm)	Systolic Blood pressure (mmHg)	Diastolic Blood Pressure (mmHg)	RR (bpm)
<50	<90	<50	<8
51-70	91-100	51-65	9-12
71-90	101-120	65-80	13-16
91-100	121-140	81-90	17-20
101-110	141-160	91-100	21-25
>110	>160	>100	>25

- Assess any correlation of range data of ambulatory preoperative VS to postoperative VS.
- Determine if specific VS ranges are associated with undesired outcomes (defined as 1) 30-day mortality, 2) hospital length of stay, c) ICU transfer rate, and 4) Rapid Response Team calls).

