## **Methods and Measures**

### **Design**

The Caretaker device is a wrist device that has a version that has already been approved by the FDA for use amongst medical professionals. For the conduct of this protocol we propose to use a newer version of the device called VitalStream, which has been cleared for use by the FDA.

The New Caretaker device being used in the study has successfully passed all safety and accuracy tests by an independent lab, which have been submitted to the FDA already (see attached Declaration of Conformity).

We plan to monitor ambulatory preoperative CareTaker VS (HR, RR, SaO2, BP, Cardiac Output, Stroke Volume, and HRV) in random patients who meet our inclusion criteria for 18-24 hours, beginning during their preoperative (Preoperative Assessment Clinic, PAC) visit then overnight after they leave. Postoperatively, we will measure these VS in the same patients for approximately 24 hours postoperatively.

These monitors transmit VS to a data cloud, where we will be able to store and then later analyze the VS data. Clinical data will be collected from our EPIC Information System in order to provide pre- and postoperative information to examine corresponding risk factors and provide demographics.

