### **Analytical Plan**

- For the feasibility portion of the study, we will describe descriptive results of subjects' time of use of the monitor, their description of ease of use (difficult or easy), and the quantity of non-artifactual VS data.
- Results will be analyzed initially using descriptive statistics (percent of time VS remained in one of the ranges listed in Table 2) and means/standard error.
- We will compare relative incidence with matched cohort undergoing surgery using univariate analyses (categorical variables: chi-square test, continuous variables: Student's t-test or Mann-Whitney U test). We will use multivariable Cox proportional hazards regression modeling to assess VS risk factors associated with the postoperative undesired outcomes mentioned in outcome measures above.
- Statistical methods data will be expressed as mean  $\pm$  SD, number (percentage), odds ratio, and 95% CI. All P values will be two-tailed, and a P value less than 0.05 is considered significant.

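### As printed, Table 2 places HR 50, SBP 90, DBP 50 and RR 8 in no range and DBP 65 in two, so the secondary time-in-range analyses omit or double-count time at those values

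*Combined protocol and SAP*

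**What the plan says.** Table 2, titled "Data Sorted into Ranges for each parameter", gives six ranges for each of four vital signs. The cells that matter here are the lowest ones and one DBP boundary:

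| Parameter | Lowest range | Second range | Third range |
|---|---|---|---|
| HR | <50 | 51-70 | 71-90 |
| SBP | <90 | 91-100 | 101-120 |
| DBP | <50 | 51-65 | 65-80 |
| RR | <8 | 9-12 | 13-16 |

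The secondary analyses rely on these ranges in four places:

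- The secondary prevalence outcome under Outcome Measure(s) points to them: "See Table 2 for ranges".
- The first bullet after the table: "Assess any correlation of range data of ambulatory preoperative VS to postoperative VS".
- The second bullet after the table: "Determine if specific VS ranges are associated with undesired outcomes".
- The Analytical Plan's initial descriptive summary: "percent of time VS remained in one of the ranges listed in Table 2".

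Neither the table nor any other section says how to treat a reading on a boundary, how readings are rounded, or at what resolution they are stored.

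**The concern.** Percent of time in range is a coherent summary only if every reading belongs to exactly one range. If some readings belong to none, a patient's percentages fall short of 100%. If some belong to two, they exceed it.

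The four gaps lie at the edge of the lowest range, which is where low values would be counted. An analyst programming the table has to decide what to do with these readings, and the plan does not say. Two analysts could each follow the plan in good faith and report different time in the lowest range. That choice would also carry into the preoperative-to-postoperative correlation and the outcome associations. If it is left until the data are in hand, it becomes a post hoc choice of cut-off.

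**Working it through.** **Step 1: enumerate the table.** I tested every whole number from 0 to 300 against the ranges, first with the lowest cell read as < (as printed), then as ≤ in case a symbol was lost when the PDF was read.

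| Parameter | In no range (<) | In two ranges (<) | In no range (≤) | In two ranges (≤) |
|---|---|---|---|---|
| HR | 50 | none | none | none |
| SBP | 90 | none | none | none |
| DBP | 50 | 65 | none | 65 |
| RR | 8 | none | none | none |

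Every other cut is contiguous for whole numbers. The DBP overlap comes from the printed digits and holds under either symbol. The other upper DBP cuts (80/81, 90/91) do not repeat a value.

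**Step 2: illustrate the size.** The plan has no figure of its own to reproduce, and it gives no means or SDs for these signs. All means and SDs below are assumptions. Readings are taken as normal and rounded to whole numbers. For boundary value k, mean m and SD s:

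- P(below k) = Φ((k − 0.5 − m)/s)
- P(equal to k) = Φ((k + 0.5 − m)/s) − Φ((k − 0.5 − m)/s)

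Time at k is what the printed table omits. It is also the gap between the two possible repairs, in which k joins either the second range or the lowest range.

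| Sign (assumed mean, SD) | Time at k (omitted) | Lowest range without k | Lowest range with k |
|---|---|---|---|
| HR (70, 12), k = 50 | 0.83% | 4.38% | 5.21% |
| SBP (110, 15), k = 90 | 1.09% | 8.59% | 9.68% |
| SBP (120, 15), k = 90 | 0.4% | 2.1% | 2.5% |
| DBP (72, 10), k = 50 | 0.36% | 1.22% | 1.58% |
| RR (14, 3), k = 8 | 1.82% | 1.51% | 3.34% |

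The RR row is a 2.2-fold difference (3.34/1.51); its components are rounded. With the same SDs and other assumed means, time at k is:

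- HR, means 65 to 80: 0.15 to 1.5 points
- SBP, means 100 to 130: 0.08 to 2.1 points
- DBP, means 60 to 80: 0.04 to 2.4 points
- RR, means 12 to 16: 0.4 to 5.5 points. The ratio is 2.7-fold at mean 16 and 1.8-fold at mean 12.

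**Step 3: the DBP total.** As printed, the DBP percentages sum to 1 − P(equal to 50) + P(equal to 65). At mean 72, SD 10 this is 1 − 0.0036 + 0.0312 = 1.028, or 102.8% (101.1 to 103.0% over means 60 to 80). With ≤ it is 1 + 0.0312 = 1.031, or 103.1% (101.3 to 104.0%). At mean 72, the 51-65 range holds 24.2% with DBP 65 and 21.1% without it; the 65-80 range holds 57.6% and 54.4%.

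**Step 4: if readings carry decimals.** Values between the printed limits, such as HR 70.4, would then also be unassigned unless rounded. Under a continuous normal at the central means, the unassigned share for RR is P(8-9) + P(12-13) + P(16-17) + P(20-21) = 2.5 + 11.7 + 9.4 + 1.3 = 24.9%. The corresponding shares are 5.1% for HR (mean 70), 5.7% for SBP (mean 110) and 3.9% for DBP (mean 72). The choice of < or ≤ does not change these shares. They apply only if values are stored or averaged with decimals and binned without rounding.

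**The case against.** The best case on the other side does not dispute the table; it argues that the point is minor.

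- **Scope.** This is a feasibility study, and its primary outcomes are data capture in both phases and monitor return (for Phase I, "Quantitate the data capture rate and how reliable our monitor return rate is in this setting"). Neither these nor the sample size uses Table 2. This stands, and it limits the weight of the point.
- **The symbol.** Four of the five faults disappear for whole numbers if < was ≤ in the source, and the text cannot settle that. This stands. Only the DBP 65 overlap is certain under either reading.
- **What the lowest-range comparison measures.** Read literally, a value of 50 is outside a range of <50, so the with-and-without figures describe disagreement between two repairs. That is right. The literal loss is time at one integer, 0.4 to 1.8% at the central assumptions. But some repair is unavoidable, and the plan does not choose one.
- **Assumed inputs.** The magnitudes rest on assumed distributions, the RR ratio sits on a small base, and the decimal figures depend on a storage format that the documents do not describe. All true. None of these figures is needed to show that the table is faulty.
- **Inference.** No changed conclusion is shown, and the Cox model in the Analytical Plan does not say that its vital-sign risk factors are the Table 2 ranges. This also stands. The two bullets after Table 2, however, explicitly tie ranges to the correlation and to outcomes.

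These limits bear on how much the fault matters. They do not make the table usable as printed.

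**Conclusion.** The concern holds. Applied literally, the stated rule drops any time at HR 50, SBP 90, DBP 50 and RR 8 and counts time at DBP 65 twice, and nothing elsewhere in the document repairs it. The DBP 65 overlap is certain; the four gaps depend on the printed < being what the source says.

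Under the assumed distributions and whole-number readings, the effect is about a point or less for HR, SBP and DBP at the central means. It is largest relative to its base for RR. The DBP double count is about 3 points at a mean of 72. If readings carry decimals and are not rounded, the unassigned share is larger. The effect on the correlations and outcome associations cannot be quantified, because that needs between-patient spread that the documents do not give. Only secondary analyses are touched.

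**What to change.** Before analysis, the sponsor should:

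1. Revise Table 2 so that the ranges are contiguous and mutually exclusive, deciding which neighbouring range holds HR 50, SBP 90, DBP 50, RR 8 and DBP 65.
2. State the resolution of the stored or averaged readings. If they are not whole numbers, add a rounding rule or define the ranges as half-open intervals.
3. Add a programming check that each patient's percentages for each parameter sum to 100% of captured time.

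The cost is one table edit, one sentence on rounding and one check. No new data are needed: the Design section says of the transmitted readings that "we will be able to store and then later analyze the VS data", so they can be re-binned.

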**Objectives**

Using a portable, wireless multi-Vital Sign (VS) monitoring system developed by Caretaker Medical, we have several objectives:

- Primary:
  - Assess the feasibility of placing a Caretaker monitor on subjects scheduled for surgery for an 18-24 hour preoperative ambulatory monitoring session.
  - Assess the feasibility of placing a Caretaker monitor on subjects scheduled for surgery for the perioperative period defined as 18-24 hour intraoperative and postoperative ambulatory monitoring session.
  - Quantitate the data capture rate (estimated at over 99% in the company's prior studies) in this setting and how reliable our monitor return rate is in this setting.
- Secondary:
  - Assess the prevalence of alterations in VS (HR, RR, SaO2, BP, Cardiac Output, Stroke Volume, and HRV preoperatively) in a group of our highest acuity patients (top quartile of risk score) undergoing non-cardiac surgical procedures requiring at least a 2-day admission.
  - Assess any correlation of concerning ambulatory preoperative VS to postoperative VS.
    - We estimate that the percent of time the patient experiences these concerning preoperative VS values will correlate with a higher risk for a similar range of VS postoperatively, as well as undesired outcomes.
      - Undesired outcomes are defined as a) 30-day mortality, b) longer length of stay, c) higher ICU transfer, and 4) RRT calls).

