### **Setting**

The subjects will be recruited in the PAC, where their monitoring period will start, and will continue at their residence (or wherever they decide to stay that night). They will return the monitor with them into the holding area on the day of their surgical procedure. We will replace their monitor on them in the Post-Anesthesia Care Unit (PACU) where it will remain with the patient for 24 hours +/- 6 hours continuously monitoring.

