## **Interventions and Interactions**

*The essential features of interventions and interactions used to generate data for the study should be described.*

- Each participant will have the study summary discussed with them, then allowed to read and sign the informed consent after having the chance to interact with the study equipment and ask questions. This will occur in the PAC prior to their preoperative visit.
- Participants who agree with entering the study will then have the CareTaker monitor placed on their left wrist and calibrated prior to them leaving the PAC.
- No surveys or questionnaires will be administered to subjects.
- An information sheet about the Caretaker device along with an emergency contact number will be given to the study subject at the time the device is placed.
- A description of the monitoring device is located in Appendix B.
- Phase I (preoperative phase) Participants will wear the CareTaker monitor for at least 12 hours (up to 24 hours) in their place of residence during the immediate time period after their initial monitor placement.
- The participants will be asked to remove the monitor and ship it back to us using pre-printed packaging or bring it with them on their day of surgery and admission to the hospital, whichever they prefer.
- For Phase II (intraoperative and postoperative phases) of the study, the participants will then have a monitor placed back on them for intraoperative and postoperative monitoring. The monitor will remain on them for up to 24 hours postoperatively, at which time a member of the research staff will remove the monitor.
- Thus, the total length of time participants will undergo active CareTaker monitoring will be 24-48 hours, divided between pre-and intra- and postoperative phases.
- Participants who complete the entire study will be compensated \$50 for their time and efforts.

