### **Data and Safety Monitoring**

Since this is a feasibility study of the Caretaker monitor, we will disable the data screen from displaying vital signs. Stored data will later be analyzed for proximity to standard vital signs measured during the subject's hospital stay. No vital signs from the monitor will be used for actionable interventions.

The principal investigator will be responsible for the overall monitoring of the data and safety of study participants. The principal investigator will be assisted by other members of the study staff.

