### **SUBSTUDY**

Since our hypotheses are 1) the percent of time the patient experiences significantly abnormal or concerning preoperative vital signs (VS) values will correlate with a higher risk for a similar range of VS postoperatively, and 2) undesired outcomes such as myocardial infarction or higher 30-day readmission rates, we need to assure that the CareTaker monitors we use have relative accuracy. This will be important to help assure that the CareTaker device measures will be generalizable to the current standards used in clinics.

In order to investigate the accuracy and precision of heart rate (HR), systolic blood pressure (SBP), diastolic blood pressure (DBP), and oxygen saturation (SpO2) measurements of the CareTaker monitoring devices we are using, we plan to compare the values obtained by CareTaker devices to standard clinic VS measurements.

In order to accomplish this, we will measure VS using hospital-grade standard monitors at intake into the Preoperative Assessment Clinic. We will then discuss the study with the patient. If the patient accepts entry to the study, we will then place the CareTaker monitor on the patient and record the VS. We will then recheck VS with standard monitors every 20 minutes while the patient is in clinic. Within 60

seconds, each VS measure will be immediately followed by recording the VS from the CareTaker monitor.

---

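### The correlation of preoperative with postoperative vital signs uses CareTaker readings on both sides, so device error that persists within a patient inflates it, and the plan's reference readings are not linked to it

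*Combined protocol and SAP*

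**What the plan says.** The Objectives expect that the percent of time spent at concerning preoperative values "will correlate with a higher risk for a similar range of VS postoperatively, as well as undesired outcomes". The list after Table 2 turns this into a secondary outcome: "Assess any correlation of range data of ambulatory preoperative VS to postoperative VS". Table 2 defines ranges for heart rate, systolic and diastolic pressure and respiratory rate only.

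Both sets of readings come from CareTaker monitors. Under Design: "Postoperatively, we will measure these VS in the same patients for approximately 24 hours postoperatively". Interventions and Interactions states that "the participants will then have a monitor placed back on them for intraoperative and postoperative monitoring", after participants have been asked to "ship it back to us using pre-printed packaging or bring it with them on their day of surgery". Calibration is described for the clinic placement only.

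Standard readings appear in two places. Data and Safety Monitoring says: "Stored data will later be analyzed for proximity to standard vital signs measured during the subject's hospital stay". The Substudy explains that "we need to assure that the CareTaker monitors we use have relative accuracy" and plans standard-monitor checks every 20 minutes in clinic for heart rate, systolic and diastolic pressure and SpO2, each followed within 60 seconds by a CareTaker reading. The Analytical Plan names no method for the pre-to-post correlation and links neither set of standard readings to it.

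**The concern.** Suppose the CareTaker reads high in a particular patient for a reason that travels with the patient, such as wrist or vessel characteristics. That patient then spends more time in the upper ranges in both phases, whatever the true values. The shared error enters both variables and adds to their covariance. A check of average accuracy would not reveal this, because mean bias can be zero while individual offsets vary.

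At stake is the interpretation of one secondary aim. A positive correlation would be read as physiological carry-over from before surgery to after it, when part of it may be reproducible device error. Cardiac output and stroke volume are most exposed, because the Substudy does not compare them with any standard.

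**Working it through.** **Inputs.** The documents give n = 150 (Sample Size) and a two-sided 0.05 level. That sample size is justified for a mean change in vital signs. No figure is given for the correlation, so there is none to reproduce. The documents give neither the between-patient SD nor the size of patient-specific device error. Both are assumed here for mean systolic pressure: true SD s = 12 or 15 mmHg in each phase, offset SD o = 2, 3, 5 or 8 mmHg.

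**Formula.** Let r be the true pre-to-post correlation and f the fraction of offset variance common to both placements. With offsets independent of true values,

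r_obs = (r·s² + f·o²) / (s² + o²).

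The chance of a significant result when the true r is 0 follows from Fisher's z: Φ(m − 1.96) + Φ(−m − 1.96), with m = atanh(r_obs)·√147.

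**Fully shared offset (f = 1).**

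| s | o | r_obs if true r = 0 | significant, n = 150 | r_obs if true r = 0.30 |
|---|---|---|---|---|
| 12 | 2 | 4/148 = 0.03 | 6.2% | 47.2/148 = 0.32 |
| 12 | 3 | 9/153 = 0.06 | 11.0% | 52.2/153 = 0.34 |
| 12 | 5 | 25/169 = 0.15 | 43.9% | 68.2/169 = 0.40 |
| 12 | 8 | 64/208 = 0.31 | 97.1% | 107.2/208 = 0.52 |
| 15 | 2 | 4/229 = 0.02 | 5.5% | 71.5/229 = 0.31 |
| 15 | 3 | 9/234 = 0.04 | 7.5% | 76.5/234 = 0.33 |
| 15 | 5 | 25/250 = 0.10 | 22.9% | 92.5/250 = 0.37 |
| 15 | 8 | 64/289 = 0.22 | 77.9% | 131.5/289 = 0.46 |

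At n = 150 a correlation above about 0.16 is significant. With s = 15, a fully shared offset reaches that alone only when o² = 225 × 0.16/0.84 = 42.9, so o is about 6.5 mmHg.

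**Partly shared or unshared offset.** Rearranging the formula gives r_obs − r = (f − r)·o²/(s² + o²). The net effect is inflation only when the shared fraction exceeds the true correlation. With o = 8 and true r = 0.30:

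- f = 0.5 gives 0.36 (s = 12) or 0.34 (s = 15);
- f = 0 gives 43.2/208 = 0.21 or 67.5/289 = 0.23, which is attenuation.

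**Check on percent of time in range.** A simulation of 2,000 trials used the Spearman correlation of percent of time above 140 mmHg, with true r = 0, s = 15, and an assumed mean of 130 and within-patient SD of 12 mmHg. With o = 8 it gave r = 0.21 and 76% significant when fully shared, 0.11 and 26% when half shared, and 0 and about 5% when unshared. The formula therefore carries over well to the form of data that the plan uses.

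**Replacing the postoperative side with standard readings.** If the standard monitor's error is unrelated to the CareTaker offset, the expected correlation is r·s/√(s² + o²). It is 0 when the true r is 0. With true r = 0.30 and o = 8 it is 3.6/14.42 = 0.25 or 4.5/17 = 0.26, before further dilution from intermittent charting.

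**The case against.** The strongest reply is that the mechanism needs error that survives two separate placements. The device is removed and later re-applied, and it is calibrated at the clinic placement. Interventions and Interactions does not guarantee the same physical unit: the first may be shipped back, although Setting speaks of the participant's own monitor. Design says that the device is cleared and has passed independent accuracy tests. The Substudy and the in-hospital comparison supply the reference data needed to examine the error. The aim is secondary, in a study whose primary outcomes are data capture and monitor return.

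Most of this stands, and it limits the point. A reader might infer that every device error creates correlation. It does not: only the persistent part does, and the rest weakens a real association. A reader might also infer that the same unit is worn twice, but the documents establish only the same device type. Unit-specific error need not carry over, though error from the patient's own anatomy could.

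The reply does not remove the point. Phase II calibration is not described, clearance gives no figure for patient-specific offsets, and neither comparison is connected to the correlation.

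**Conclusion.** The concern holds as a gap in the analysis of a secondary outcome. Persistent patient-specific CareTaker error inflates the planned correlation, and nothing in the Analytical Plan deals with it. The size rests wholly on assumed SDs and on how much of the offset is shared: negligible at 2 to 3 mmHg, material at 8 mmHg if fully shared.

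Two stronger readings are not supported. One is that the device alone would manufacture the finding. That needs a large, fully shared offset and a true correlation of zero within the same patients, which is unlikely. Inflation of a real correlation is the more realistic problem. The other is that carry-over can never be told apart from device error. For heart rate, blood pressure and SpO2 the plan already collects readings that allow the error to be examined. The primary feasibility outcomes are unaffected.

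**What to change.** Add to the Analytical Plan:

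- **A sensitivity analysis.** For heart rate, systolic and diastolic pressure, and for respiratory rate and SpO2 where charted, correlate preoperative CareTaker data with standard in-hospital readings from the postoperative monitoring window. Report it beside the CareTaker-to-CareTaker correlation and interpret carry-over in light of both. Do not set a pass/fail agreement rule: the two are expected to differ even when carry-over is real (0.46 to 0.52 against 0.25 to 0.26 in the 8 mmHg example with a true 0.30).
- **Persistence of the offset.** Compute each patient's CareTaker-minus-standard difference from the clinic pairs and from time-matched hospital readings, and report how far it persists. This is possible for heart rate, systolic and diastolic pressure and SpO2. Respiratory rate is not in the clinic comparison.
- **A caveat.** State that any cardiac output or stroke volume correlation without a standard reading may partly reflect reproducible device error.

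The cost is a few sentences of plan and some analysis of readings that the plan already intends to use, with no new patients or visits. The drawback is that charted readings are intermittent, so the sensitivity correlation is diluted and is not an exact percent-of-time measure. It also removes only error that the CareTaker does not share with the standard monitor.

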## **Subjects selection criteria**

- **Inclusion Criteria**

- Age > 18 years
- Scheduled for surgery from an outpatient setting and scheduled for a pre-admission PAC appointment
- Risk stratification placing them in the top 25th percentile using our internally-validated PAC Risk Score.

- **Exclusion Criteria**

- Surgery on the day of admission (same-day surgery)
- Any upper extremity surgery

- **Sample Size**

- Our power analysis indicates that we need a total number of 150 patients to have at least 90% power in detecting a change in VS assuming a mean population VS (HR or BP) change of 12% from Phase 1 to Phase 2. We estimate a standard deviation of 10%, a type I error rate (2-sided) of 5%, and 1% missing follow-up data. We may have to consent up to 200 subjects in order to obtain the 150 evaluable subjects.
- We estimate this study lasting up to 12 months.

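### Correlating time in fixed Table 2 ranges can show almost no preoperative-to-postoperative carry-over in a heavily occupied middle range, even when patients' levels carry over strongly

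*Combined protocol and SAP*

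**What the plan says.** The Objectives section expects that the percent of time spent in concerning preoperative values "will correlate with a higher risk for a similar range of VS postoperatively, as well as undesired outcomes". The secondary outcomes listed with Table 2 turn this into an instruction to "Assess any correlation of range data of ambulatory preoperative VS to postoperative VS". Table 2 gives six ranges each for heart rate, systolic pressure, diastolic pressure and respiratory rate; in each column the four inner ranges are bounded and the two outer ones are open-ended.

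The Analytical Plan begins with descriptive statistics, namely "percent of time VS remained in one of the ranges listed in Table 2) and means/standard error". It names no correlation coefficient, does not say which preoperative quantity is paired with which postoperative one, and specifies no correlation of patient means.

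The sample size paragraph under Subjects selection criteria is framed as "assuming a mean population VS (HR or BP) change of 12% from Phase 1 to Phase 2", with an estimated SD of 10%. It gives no direction for the change and does not say whether the 10% is the SD of the change or the SD between patients.

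**The concern.** Two features of the range data work against a correlation.

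- **Shape.** Patients whose level is well above a middle range and patients whose level is well below it both spend little time in it. Time in that range is therefore not a steady function of level.
- **Shift.** If the population moves by 12% between phases, the same fixed range picks out different patients before and after surgery, even when every patient keeps his or her rank. A correlation of patient means is unaffected by a uniform shift.

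At stake is how a secondary objective is read. A near-zero coefficient in the range where patients spend most of their time could be reported as no carry-over when levels carry over well, and neighbouring ranges could appear to disagree only because of where the cuts fall.

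**Working it through.** **The plan's own figure.** The documents give no power or effect size for the correlation. The 150 patients are tied to detecting the 12% mean change. For a paired comparison, n = [SD × (1.960 + 1.282) / change]² = (10 × 3.242 / 12)² = 7.3, so 8 patients (10 by paired t, 11 with 1% missing). The 150 is thus not reproduced from its inputs, but that is a separate matter. For a correlation, 150 × 0.99 gives 148 evaluable patients, and Fisher's z gives about 90% power at r of about 0.26. Sample size is not the limitation here.

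**Inputs.** From the documents: the Table 2 cuts, the 12% change, the 10% SD (read here as the SD of the change), n = 150, two-sided 5%. Assumed, not in the documents: SBP mean 130, between-patient SD 15, within-patient SD 12; HR mean 75, SDs 11 and 8; normal values within patient.

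**Implied correlation of patient means**, with equal variances: r = 1 − (0.10 × mean)² / (2 × SD²).
- SBP: 1 − 13² / (2 × 15²) = 1 − 169/450 = 0.62
- HR: 1 − 7.5² / (2 × 11²) = 1 − 56.25/242 = 0.77

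**Mechanism by hand.** Take three patients with SBP means one SD below, at, and one SD above 130, and let all rise by exactly 15.6 (12% of 130), so that levels correlate perfectly. Time in 121-140 is Φ((140.5 − m)/12) − Φ((120.5 − m)/12).

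| Preoperative mean | Time in range before | Postoperative mean | Time in range after |
|---|---|---|---|
| 115 | 31% | 130.6 | 60% |
| 130 | 60% | 145.6 | 32% |
| 145 | 33% | 160.6 | 5% |

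The correlation of the two time-in-range columns is about −0.09, although the levels correlate at 1.

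**Simulation of 150-patient trials** (patient means bivariate normal with the r above; same-range Pearson correlation):

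| Range | No shift | +12% | −12% |
|---|---|---|---|
| SBP 121-140 | – | r 0.06, power 10% | r 0.08, power 17% |
| SBP 141-160 | – | r 0.21, power 72% | – |
| SBP 101-120 | – | power about 100% | power 57% |
| SBP <90 | r 0.39 | r 0.32 to 0.33, power 75% | r 0.43 |
| SBP >160 | r 0.48 | r 0.48, power about 100% | – |
| HR 51-70 | – | – | r 0.42, power 100% |
| HR 71-90 | – | r 0.13 to 0.15, power 37% to 39% | r 0.42, power 100% |
| HR >110 | r 0.46 | r 0.51 | r 0.39, power 74% |
| Patient means | SBP 0.62, HR 0.77 | unchanged, power 100% | unchanged, power 100% |

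Spearman gives the same answer in the two affected ranges at +12%: 0.06 (power 12%) for SBP 121-140 and 0.10 (power 22%) for HR 71-90. In the outer ranges Spearman has about 100% power under either shift.

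**How occupied the affected ranges are.** The total preoperative SD is √(15² + 12²) = 19.2 for SBP and √(11² + 8²) = 13.6 for HR. The share of time is Φ(10.5/19.2) − Φ(−9.5/19.2) = about 40% in SBP 121-140, and Φ(15.5/13.6) − Φ(−4.5/13.6) = about 50% in HR 71-90.

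**Sensitivity.** Over a wider grid (SBP mean 120 to 140, HR mean 70 to 80, correlation of means 0.4 to 0.8, within-patient SD 8% or 14% of the mean, shift of 12% either way), the share of the continuous r that a same-range correlation keeps is:
- weaker of the third and fourth Table 2 ranges, Pearson: median 20% (quartiles 5% to 39%, range −34% to 77%)
- stronger of those two, Pearson: median 65% (range 30% to 90%)
- lowest and highest ranges, Pearson: median 67% (range 2% to 93%)
- lowest and highest ranges, Spearman: median 97% (range 82% to 98%)

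**The case against.** **The effect is selective.** A reader might infer that the correlation vanishes across the central ranges and weakens in the outer ones. The documents do not support that. Usually one central range collapses, sometimes two, and in the HR example at −12% none does. The outer-range loss is mostly a property of Pearson correlation on skewed percentages near zero, and much of it is there without any shift. No section prescribes Pearson. This stands.

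**Row-by-row pairing is one reading.** The wording under Table 2 requires only the preoperative side to be range data, and the Objectives speak of a similar range, not the identical row. If preoperative time in range is correlated with the postoperative mean, a uniform shift has no effect. This stands as to the shift but does not remove the problem: SBP 121-140 then gives r of about 0.03 at every shift, zero included, because of the shape alone.

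**The hypothesis concerns extremes.** Time in concerning values is a legitimate question, those values would be expected to lie in the outer ranges, and a patient mean can hide excursions. This stands, and it rules out replacing the range analysis with means.

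**The stakes are limited.** The primary outcomes are data capture and monitor return, the correlation carries no power target, and means are reported anyway, so no data are lost. This also stands; it keeps the point a modest one.

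**Conclusion.** The point holds in limited form. As written, the range-based correlation can come out close to zero in a central, heavily occupied range while patients' levels carry over strongly: about 0.06 against 0.62 for SBP 121-140, and about 0.15 against 0.77 for HR 71-90, both at +12%. These sizes rest on assumed means and SDs, on reading the 10% as the SD of the change, and on same-range pairing; the 12% and 10% figures apply to HR or BP only. The affected range cannot be predicted from the documents, which give neither a baseline mean nor a direction of change.

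It does not follow that the range analysis is unsound as a whole, or that means should take its place. Rank correlation on the outer ranges largely preserves the signal, and that is where the concerning-values hypothesis sits. This is a cheap improvement to a secondary analysis, not a threat to the trial's primary aims.

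**What to change.** Amend the correlation bullet under Table 2, and the Analytical Plan to match, as follows:

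- **Overall carry-over (added).** For each vital sign, estimate the association between each patient's time-weighted Phase 1 mean and Phase 2 postoperative mean, as a correlation with 95% CI and a linear regression of the postoperative mean on the preoperative mean.
- **Concerning values (kept).** Relate preoperative to postoperative percent of time in the outer, open-ended ranges by Spearman correlation, and state the pairing explicitly.
- **Middle ranges.** Report percent of time descriptively, and state that a null correlation there will not be read as absence of carry-over.

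The cost is some plan wording and a little extra analysis, with no new data or patients. The downside is that a mean can miss brief extremes, which is why the outer-range analysis stays.
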